11.2.2 Subjects to Analyze

The decision as to which plasma samples collected will be assayed for evaluation of pharmacokinetics/pharmacodynamics will be collaboratively determined by the Departments of Quantitative Pharmacology and Pharmacometrics and the appropriate department within Early-Stage

Development. If indicated, these samples may also be assayed and/or pooled for assay in an exploratory manner for metabolites and/or additional pharmacodynamic markers.

The following populations are defined for the analysis and reporting of data. All subjects will be reported, and their data analyzed, according to the treatment they actually received.

All Subjects as Treated: All subjects who received at least one dose of the investigational drug. This population will be used for assessments of safety and tolerability.

Per-Protocol: The set of data generated by the subset of subjects who comply with the protocol sufficiently to ensure that these data will be likely to exhibit the effects of treatment, according to the underlying scientific model. Compliance covers such considerations as exposure to treatment, availability of measurements and absence of major protocol violations. Any subjects or data values excluded from analysis will be identified, along with their reason for exclusion, in the CSR. At the end of the study, all subjects who are compliant with the study procedure as aforementioned and have available data will be included in the primary analysis dataset. This population will be used for the pharmacokinetic analyses.

11.2.3 Analysis Overview

11.2.3.1 Primary Analysis: Regression Analysis

For this analysis, all the data from Part 1 will be included.

In addition to running the primary regression analysis below using BSA normalized eGFR as the measure of renal function for each subject, the analysis will also be run using BSA un-normalized eGFR and CLcr from C-G equation.

Separately for each pharmacokinetic parameter, individual values of AUC $0-\infty$, AUC $0-\text{last}$, C_{max}, CL/F, and CL_r will be evaluated with a linear mixed effects model containing eGFR as a continuous variable. The subject's mean renal function value derived from 2 serum creatinine measurements at Screening will be used for the analysis. Estimates of the slope and intercept, together with corresponding 95% confidence intervals will be obtained. The estimated mean and corresponding 95% confidence interval for each RI group will be predicted at the midpoint of the defined eGFR range for each group (45, and 22.5 for moderate, and severe, respectively). However, for the normal renal function group, the estimated mean and corresponding 95% confidence interval will be predicted at the median of the observed eGFR values. Sample SAS code is given below:

```
Proc mixed data=pk ;
model PK= eGFR / s cl DDFM=KR alpha=0.05 outpm=normres ;
estimate "predicted PK in severe" int 1 eGFR 22.5/alpha=0.1 cl e;
estimate "predicted PK in moderate" int 1 eGFR 45/alpha=0.1 cl e;
estimate "predicted PK in mild" int 1 eGFR 75/alpha=0.1 cl e;
estimate "predicted PK in normal" int 1 eGFR xx /alpha=0.1 cl e;
      xx is median eGFR for healthy matched control subject group;
run;
```

The data will be examined for departures from the assumptions of the model. The residuals from the model will be examined for normality using diagnostic plots such as residuals vs predicted values and normal probability plots of residuals. Lack of fit will also be visually assessed.

If the model used does not fit the data adequately, other models, such as natural log transformed pharmacokinetic versus renal function or natural log transformed pharmacokinetic versus natural log transformed renal function, will be explored. Other transformations or non-linear models will also be considered.

Additionally, plots of MK-7264 pharmacokinetic parameter values AUC_{0-∞}, AUC_{0-last}, C_{max}, CL/F, and CL_r versus eGFR along with a regression line and 95% confidence bands for regression line will be constructed. Different symbols will be used to identify different renal function groups. Additionally, separate plots of AUC_{0-∞} and C_{max} values vs age and body weight will be provided

Individual values will be listed for each PK parameter (AUC_{0-∞}, AUC_{0-last}, AUC₀₋₁₂, AUC₀₋₂₄, AUC₀₋₄₈, C_{max}, T_{max}, CL/F, V_z/F, apparent terminal t_{1/2}, A_{e0-24}, A_{e0-48}, and F_e) by population, and the following (non-model-based) descriptive statistics will be provided: N (number of subjects with non-missing data), arithmetic mean, standard deviation, arithmetic percent CV (calculated as 100 x standard deviation/ arithmetic mean), median, minimum, maximum, geometric mean, and geometric percent CV (calculated as 100 x sqrt(exp(s²) - 1), where s² is the observed variance on the natural log-scale).

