9.8.3 Statistical/Analytical Methods and Issues

Pharmacokinetics

The plasma PK of MK-7264 administered to subjects with varying degrees of RI was compared to healthy matched control subjects using regression and categorical analysis.

Regression Analysis (Part 1)

Separately, individual values of AUC_{0-last}, AUC_{0-∞}, C_{max}, CL/F, and CL_r were ln-transformed and evaluated with a linear fixed-effects model containing eGFR as a continuous variable. The subject's mean renal function value derived from 2 serum creatinine

measurements at screening were used for the analysis. Estimates of the slope and intercept, together with corresponding 95% confidence intervals (CI) were obtained. The estimated mean and corresponding 95% CI for each RI group were predicted at the mid-point of the defined eGFR range for each group (45 mL/min/1.73 m² for moderate and 22.5 mL/min/1.73 m² for severe). Although subjects with mild RI were not enrolled in this study, the PK of MK-7264 were also predicted in this population at the eGFR of 75 mL/min/1.73 m² (the midpoint of the eGFR range for mild RI of 60 - 89 mL/min/1.73 m²). For the healthy population, the estimated mean and corresponding 95% CI were predicted at the median of the observed eGFR values. The predicted means and corresponding 95% CIs were exponentiated to obtain estimates on the original scale. In addition to running the regression analysis using BSA normalized eGFR as the measure of renal function for each subject, the analysis was also run using BSA non-normalized eGFR and CrCL from the Cockcroft-Gault (C-G) equation.

Categorical Analysis (Part 1 and Part 2 Period 1)

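### The primary regression text asks for 95% intervals for the predicted group means, but every ESTIMATE line in its sample code requests 90% limits

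*Protocol*

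**What the plan says.** Protocol section 11.2.3.1 sets the level in prose. For the impaired groups: "The estimated mean and corresponding 95% confidence interval for each RI group will be predicted at the midpoint of the defined eGFR range", with midpoints of 45 (moderate) and 22.5 (severe). For the controls: "for the normal renal function group, the estimated mean and corresponding 95% confidence interval will be predicted at the median" of their observed eGFR. The slope and intercept are also to have 95% intervals.

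The sample code in the same section reads:

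- MODEL line: "model PK= eGFR / s cl DDFM=KR alpha=0.05 outpm=normres"
- severe: "int 1 eGFR 22.5/alpha=0.1 cl e"
- moderate: "int 1 eGFR 45/alpha=0.1 cl e"
- mild: "int 1 eGFR 75/alpha=0.1 cl e"
- normal: "int 1 eGFR xx /alpha=0.1 cl e"

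Later in the section, the plot of each parameter against eGFR is to show 95% confidence bands for the regression line.

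SAP section 9.8.3 repeats the level: "The estimated mean and corresponding 95% CI for each RI group were predicted at the mid-point of the defined eGFR range". It states 95% for the healthy group too. It adds a prediction for mild impairment at eGFR 75, then says that the predicted means and their 95% intervals were exponentiated.

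**The concern.** The text and the code in one section give different confidence levels for the same output. The MODEL line follows the prose; the ESTIMATE lines do not. The output concerned is the predicted mean exposure and clearance by renal function, from the analysis that the protocol labels primary.

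If the alpha options are carried into the production program, 90% limits would appear under a 95% heading. The tabulated limits would then be narrower than the plotted 95% band at the same eGFR, and a reader could not detect the error from the label.

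**Working it through.** **1. Which option controls which limits.** The `alpha=` on MODEL sets the level for the fixed-effect solution, here the intercept and slope. The `alpha=` on an ESTIMATE statement sets the level for that estimate and is not overridden by the MODEL line. The limits are two-sided, so reading 0.1 as a one-sided 5% does not recover a 95% interval.

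**2. Levels side by side.**

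| Quantity | Protocol text | Sample code | SAP text |
|---|---|---|---|
| Slope, intercept | 95% | 95% | 95% |
| Severe, moderate means | 95% | 90% | 95% |
| Normal mean | 95% | 90% | 95% |
| Mild mean | not planned | 90% | 95%, through the sentence on exponentiation |

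No text asks for 90% limits on these predictions. The documents use 90% for geometric mean ratios: in the precision calculation (protocol 11.2.1), the categorical analysis (protocol 11.2.3.2, SAP 9.8.3) and the dialysis comparison (protocol 11.2.3.3, SAP 9.8.3).

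**3. Degrees of freedom.** The regression uses Part 1 only: 6 severe + 6 moderate + 6 healthy = 18 subjects, all of whom completed (SAP 10.1). With an intercept, a slope and one residual variance, df = 18 − 2 = 16.

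**4. Interval width.** Limits are estimate ± t(1 − alpha/2, df) × SE.

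- As the text specifies: t(0.975, 16) = 2.1199
- As coded: t(0.95, 16) = 1.7459
- Ratio: 1.7459 / 2.1199 = 0.8236, so the coded intervals are 17.6% too short
- Inverse: 2.1199 / 1.7459 = 1.214, so the correct intervals are 21% wider than coded

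If a parameter is missing for one, two or three subjects, the shortfall is 17.8%, 17.9% or 18.0%.

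**5. Coverage.** A simulation of 40,000 data sets, with assumed eGFR values spread evenly within each group, gave coverage of 89.7% to 90.1% for the coded limits across the four prediction points. At `alpha=0.05` coverage was 94.8% to 95.0%.

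**6. Illustration in residual-SD units.** Observed eGFR values are not given, so assume six subjects each at 22.5, 45 and 100. The mean is 55.83 and Sxx = 6 × (33.33² + 10.83² + 44.17²) ≈ 19,075. Then SE/SD = √(1/18 + (x₀ − 55.83)²/Sxx).

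| Group | SE/SD | Half-width as coded (× 1.7459) | Half-width at 95% (× 2.1199) |
|---|---|---|---|
| Severe | 0.337 | 0.59 | 0.72 |
| Moderate | 0.248 | 0.43 | 0.53 |
| Normal | 0.397 | 0.69 | 0.84 |

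Moving the assumed group values over 15–25, 38–52 and 90–110 puts the severe half-width at 0.52–0.66 as coded and 0.64–0.80 at 95%. The 17.6% does not depend on these placements.

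**7. Number of intervals.** Five parameters × three groups = 15 for each renal-function measure, or 5 × 4 = 20 if mild is counted through the SAP.

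**The case against.** The block is labelled sample code and cannot run as printed: it holds a placeholder for the control median and an uncommented explanatory line. A programmer must edit it, with the 95% instruction directly above. The SAP, written in the past tense, says 95%. It also describes log-transformed parameters in a fixed-effects model, whereas the protocol describes a mixed-effects model on untransformed values, so the block was evidently not used unchanged. No hypothesis is tested (SAP 9.8.3.3), and the comparisons with controls come from the categorical ratios, whose 90% level is intended. No rule in the documents turns on the width of these intervals.

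Much of this stands, and it limits the consequence. The absence of the point from SAP section 9.9 is weak evidence, since running 95% limits as the text planned would not be a change. For mild, the conflict rests on the SAP alone, because the protocol text plans no such prediction.

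The inconsistency itself remains. Filling in the placeholder, removing the stray line and log-transforming the response all leave `alpha=0.1` in place. The SAP's statement of 95% gives the intended level; it does not show which option was run.

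**Conclusion.** The concern holds. Three ESTIMATE lines contradict the protocol's own text, and the fourth, for mild, conflicts with the SAP. Run with those options, the code gives 90% limits where 95% are specified: 17.6% too short on the scale on which the model is fitted, with twice the nominal non-coverage. That figure assumes 18 analysed subjects and a single residual variance, and it changes little with a few missing values.

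The effect is confined to interval width. Point estimates, slope, intercept and categorical ratios do not change. Whether any reported interval was produced at 90% cannot be settled from these documents. It should be corrected because the intervals belong to the analysis labelled primary and the fault would not show in the output.

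**What to change.** Set `alpha=0.05` on all four ESTIMATE lines, so that the code agrees with the protocol text, the SAP and the plotted 95% bands. Then check the production program or output for the level actually used in the predicted-mean intervals, for all three renal-function measures. Rerun or relabel any that were produced at 90%.

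The cost is four edits and one check of the output, with no new data. The intervals become about 21% wider than those the sample code would give.

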11.2.3.2 Secondary Analysis: Categorical Analysis

Separately for each pharmacokinetic parameter, individual values of AUC_{0-∞}, AUC_{0-last}, C_{max}, CL/F, and CL_r (as appropriate) will be natural log-transformed and evaluated with a linear fixed-effects model containing a categorical effect for population (ESRD renal impairment Period 1 of Part 2, severe RI, moderate RI, and healthy matched control, based on BSA normalized eGFR). The REPEATED statement with the GROUP=Population option will be used in SAS PROC MIXED to estimate separate variances for each population. The Kenward and Roger adjustment will be used to calculate the denominator degrees of freedom for the fixed-effect (DDFM=KR). Ninety-five percent (95%) confidence intervals for the least squares means for each population will be constructed on the natural log scale and will reference the t-distribution. Exponentiating the least-squares means and their corresponding 95% confidence intervals will yield estimates for the population geometric means and confidence intervals about the geometric means on the original scale. Sample SAS code is given below:

```
Proc mixed =data;
CLASS Population Subject;
MODEL lnPk = Population / DDFM=KR;
REPEATED / GROUP=Population;
LSMEANS Population / CL;
run;
```

To compare subjects with RI in each of the renal categories to subjects with normal renal function, a two sided 90% confidence interval for the true difference in means (renal impairment – normal renal function) will be calculated for each PK parameters (AUC_{0-∞}, AUC_{0-last}, C_{max}, CL_r, and CL/F) using the mean square error from the model and referencing a t-distribution. For each of the RI populations, these confidence limits will be exponentiated to obtain the 90% confidence interval for the true ratio of geometric means (renal impairment/normal renal function) for each pharmacokinetic parameter.

Figures showing individual pharmacokinetic values with GMs (95% confidence intervals) by population, plotted on the natural log scale, will be provided for AUC_{0-∞}, AUC_{0-last}, Cmax, CL/F, and CL_r.

Summary Statistics using BSA un-normalized eGFR: The subjects will be re-categorized into different renal categories based on their BSA un-normalized eGFR and non-model based summary statistics by population will be provided for (AUC_{0-∞}, AUC_{0-last}, AUC₀₋₁₂, AUC₀₋₂₄, AUC₀₋₄₈, Cmax, Tmax, CL/F, Vz/F, apparent terminal t_{1/2}, Ae₀₋₂₄, Ae₀₋₄₈, and Fe, as applicable).

Analysis using CL_{cr} (C-G equation): The subjects will be re-categorized into different renal categories based on their CL_{cr} obtained from C-G equation and non-model based summary statistics by population will be provided for (AUC_{0-∞}, AUC_{0-last}, AUC₀₋₁₂, AUC₀₋₂₄, AUC₀₋₄₈, Cmax, Tmax, CL/F, Vz/F, apparent terminal t_{1/2}, Ae₀₋₂₄, Ae₀₋₄₈, and Fe, as applicable).

11.2.3.3 ESRD Requiring Hemodialysis (Part 2)

To evaluate the extent to which MK-7264 is removed from plasma by hemodialysis, a linear mixed effect model with population (ESRD RI Period 1, ESRD Period 2) as a fixed effect will be used. An unstructured covariance matrix will be used to allow for unequal treatment variances and to model the correlation between the two treatment measurements within each subject via the REPEATED statement in SAS PROC MIXED. Kenward and Roger's method will be used to calculate the denominator degrees of freedom for the fixed effects (DDFM=KR).

A natural log transformation will be applied to CL/F, AUC_{0-∞}, AUC_{0-last}, and Cmax. For each PK parameter, 95% confidence intervals for the least squares mean will be constructed on the natural log scale and will reference the t-distribution. Exponentiating the least-squares means and their corresponding 95% confidence intervals will yield estimates for the population geometric means and confidence intervals about the geometric means on the original scale.

A two sided 90% confidence interval for the true difference in means (ESRD RI in Period 2 -ESRD RI in Period 1) will be calculated for each PK parameter (AUC_{0-∞}, AUC_{0-last}, Cmax, and CL/F) using the mean square error from the model and referencing a t-distribution. These confidence limits will be exponentiated to obtain the 90% confidence interval for the true ratio (GMR) of geometric means (ESRD RI in Period 2 of Part 2 / ESRD RI in Period 1 of Part 2) for each pharmacokinetic parameter.

Sample SAS code is given below:

```
proc mixed data=dataset;
  class population subject;
  model endpoint = population/ddfm=kr;
  repeated /type=UN subject=subject group=population;
  run;
```

Plots with individual ratios overlaid with GMR and corresponding 90% CI will be provided for CL/F, AUC_{0-∞}, AUClast, and Cmax

Individual listings and descriptive statistics for AUCD, AUC(2.5-6)Ca, AUC(2.5-6)Cv, CLD plasma, CLD,dialysate, AD, and AD,total following a single-dose administration of MK-7264 will be provided for subjects with ESRD.

Individual listings and descriptive summary statistics may be provided for CLr for ESRD subjects, if CLr could be determined in these subjects.

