7.2.3 Rationale for Endpoints

The primary objective of this study is to evaluate the pharmacokinetic profile of MK-7264 in subjects with impaired renal function. This study will compare the overall pharmacokinetic profile of MK-7264 in subjects with impaired renal function to that of healthy subjects, and this will be assessed by overall exposure (AUC $0-\infty$), C_{max}, CL/F and CL_r.

For ESRD subjects only, CLD,plasma, CLD,dialysate, AD, and AD,total will provide a measure of the extent of MK-7264 removal by HD.

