Separately, individual values of AUC_{0-last}, AUC_{0-∞}, C_{max}, CL/F, and CL_r were ln-transformed and evaluated with a linear fixed-effects model containing a categorical effect for population (ESRD Non-HD, severe RI, moderate RI, and healthy matched control, based on BSA normalized eGFR). The REPEATED statement with the GROUP=Population option was used in SAS PROC MIXED to estimate separate variances for each population. The Kenward-Roger adjustment was used to calculate the denominator degrees of freedom for the fixed-effect (DDFM=KR). Ninety-five percent (95%) CI for the least-squares means for each population were constructed on the ln-scale and referenced to the t-distribution. The least-squares means (LSM) and their corresponding 95% CI were exponentiated to yield estimates for the population geometric means (GM) and CI about the GM on the original scale. To compare subjects with RI in each of the renal categories to subjects with normal renal function, a two-sided 90% CI for the true difference in means (renal impairment – normal renal function) was calculated for each PK parameter (AUC_{0-last}, AUC_{0-∞}, C_{max}, CL_r, and CL/F) using the mean square error from the model and referencing a t-distribution. For each of the RI populations, these confidence limits were exponentiated to obtain the 90% CI for the true GMR renal impairment/normal renal function) for each PK parameter. Figures showing individual PK values with GMs (95% CI) by population, were provided for AUC_{0-last}, AUC_{0-∞}, C_{max}, CL/F, and CL_r.

ESRD HD vs ESRD Non-HD (Part 2)

To evaluate the extent of MK-7264 removal by HD in Part 2, a linear mixed-effects model with population (ESRD Non-HD, ESRD HD) as a fixed effect was used. An unstructured covariance matrix was used to allow for unequal variances and to model the correlation between the two measurements within each subject via the REPEATED statement in SAS PROC MIXED. The Kenward-Roger adjustment was used to calculate the denominator degrees of freedom for the fixed-effects (DDFM=KR). A ln-transformation was applied to AUC_{0-last}, AUC_{0-∞}, C_{max}, and CL/F. For each PK parameter, 95% CIs for the LSMs was constructed on the ln-scale and referenced the t-distribution. The LSMs and corresponding 95% CIs were then exponentiated to obtain population GM and CI about the GM on the

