original scale. A two sided 90% CI for the true difference in means (ESRD HD - ESRD Non-HD) was calculated for each PK parameter (AUC0-last, AUC0- ∞ , Cmax, and CL/F) using the mean square error from the model and referencing a t-distribution. These confidence limits were exponentiated to obtain the 90% CI for the GMR (ESRD HD / ESRD Non-HD) for each PK parameter.

Other Pharmacokinetic Analyses

Subjects with moderate and severe RI and healthy matched control subjects (based on their BSA normalized eGFR) were re-categorized into different renal categories based on their BSA non-normalized eGFR and CrCL. Non-model based summary statistics by population were provided for AUC0-last, AUC0- ∞ , Cmax, CL/F and CLr.

Non-model-based %CV of the GM were presented for plasma MK-7264 AUC0-12, AUC0-24, AUC0-48, apparent terminal $t_{1/2}$, and Vz/F for subjects with moderate and severe RI, ESRD Non-HD, ESRD HD, and healthy matched control subjects. Individual values were also listed for each PK parameter by population and non-model-based descriptive statistics were provided.

Arithmetic mean (AM) concentration-time plots (with and without standard deviation [SD] error bars) of plasma, pre- and post-dialyzer plasma, and dialysate MK-7264 were presented by population on a linear-linear scale plot with an inset semi-log scale plot. The BLQ values were treated as 0 for the calculation of the AM (and SD, as appropriate). At the beginning of the profile, if < 50% of subjects had a quantifiable concentration \geq LLOQ for a given time point, the AM concentration was presented as 0. At the end of the profile when concentrations from some subjects began to fall BLQ, the AM value was only plotted if \geq 50% of subjects had quantifiable concentrations \geq LLOQ and the AM value was \geq LLOQ. However, all AM values were presented in the concentration tables. A reference line for the LLOQ value was added to the plot, where possible, as well as a footnote indicating the AM concentrations at or after certain time points that were not presented since > 50% of subjects had values < LLOQ or the AM was < LLOQ.

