9.9 Changes in the Planned Analyses

One (1) subject with ESRD had 6 missing peripheral blood samples (Part 2, Period 1) due to difficult venipuncture. This 1 subject was excluded from the primary PK analyses presented in [Section 11](#). Supplementary analysis including all 6 subjects is shown in [Section 14](#).

One (1) dialysate sample was missing for 3 subjects (4-hour for 1 subject; 4.5-hour for 2 subjects) as they were mistakenly not processed and discarded; therefore, the AD and rr values at these time points could not be determined. In addition, a sensitivity analysis was performed and it was determined that the missing sample had minimal impact ($\leq 1\%$) on the extent of removal of MK-7264 by HD; therefore, a decision was made to include all subjects in the analysis.

Five (5) of the 6 ESRD subjects did not produce urine; therefore, PK parameters in Periods 1 and 2 of Part 2 could not be calculated. Although the remaining subject did produce urine, MK-7264 concentrations in urine were not quantifiable.

For Part 1, the protocol classified the categorical analysis as a secondary analysis; however, when Part 2 was added, it was considered as a part of the primary analysis used to assess the primary PK objective in ESRD subjects, and was described as such in the statistical analysis plan.

The protocol stated that dialysate samples would be collected pre- and post-HD, as well as for 1 minute every half hour during HD; however, as dialysate is a product of HD, no pre- or post-HD samples were obtained.

Non-model based summary statistics by population based on BSA normalized eGFR were provided for both primary (AUC_{0-∞}, AUC_{0-last}, C_{max}, CL/F, and CL_r) and exploratory endpoints (AUC₀₋₁₂, AUC₀₋₂₄, AUC₀₋₄₈, T_{max}, V_{z/F}, apparent terminal t_{1/2}, Ae₀₋₁₂, Ae₁₂₋₂₄, Ae₂₄₋₄₈, Ae₀₋₂₄, Ae₀₋₄₈, Fe₀₋₁₂, Fe₁₂₋₂₄, Fe₂₄₋₄₈, Fe₀₋₂₄ and Fe₀₋₄₈). However, non-model based summary statistics by population based BSA non-normalized eGFR and CrCL using C-G equation were provided only for primary AUC_{0-∞}, AUC_{0-last}, C_{max}, CL/F and CL_r, as some categories had few or no subjects.

There were no other changes to the planned analyses of the original protocol [16.1.1.4].

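### The Part 2 sample code (protocol 11.2.3.3) adds GROUP=population to TYPE=UN and so drops the within-subject covariance that the text says is modelled

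*Protocol*

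**What the plan says.** Protocol section 11.2.3.3 sets out a mixed model for the extent of removal by hemodialysis. Its one fixed effect, population, has two levels: ESRD Period 1 (no dialysis after dosing) and ESRD Period 2 (dialysis starting two hours after dosing). The same subjects supply both levels.

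- **Covariance, in the text.** The unstructured matrix is to allow unequal variances and "to model the correlation between the two treatment measurements within each subject via the REPEATED statement in SAS PROC MIXED".
- **Covariance, in the code.** The sample code beneath has "repeated /type=UN subject=subject group=population". The MODEL line contains population only, with Kenward-Roger degrees of freedom. There is no RANDOM statement and no repeated effect is named.
- **Intervals, in the text.** For the means, "95% confidence intervals for the least squares mean will be constructed on the natural log scale". For Period 2 minus Period 1, "A two sided 90% confidence interval for the true difference in means" is then exponentiated to give limits for the GMR. The code requests neither interval.
- **SAP section 9.8.3.** It reports that "An unstructured covariance matrix was used to allow for unequal variances and to model the correlation between the two measurements within each subject" and that the 90% limits were obtained "using the mean square error from the model and referencing a t-distribution". It shows no code.
- **SAP section 9.9.** One ESRD subject had six missing peripheral samples in Period 1. "This 1 subject was excluded from the primary PK analyses", which leaves five pairs; all six are in a supplementary analysis.

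**The concern.** In PROC MIXED, GROUP= gives each level of the grouping factor its own covariance parameters, with no covariance across levels. That suits the categorical analysis in protocol section 11.2.3.2, where each subject belongs to one population. In Part 2 the factor changes within subject, so the option removes the very covariance the text asks for. TYPE=UN alone already supplies two variances and their covariance, so GROUP= adds nothing.

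Removal by hemodialysis is a primary objective of Part 2, and this model gives the only model-based estimate for it. Protocol section 7.2.3 says of the dialysis clearance and recovery parameters that they "will provide a measure of the extent of MK-7264 removal by HD", but these are summarised descriptively and are not affected. What is at stake is the 90% interval for the dialysis/non-dialysis ratio and the precision gained by using each subject as their own control, in an analysis set of five.

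**Working it through.** The documents give no precision figure for the Part 2 contrast, so there is none to reproduce there. As a check on method, protocol Table 4 for AUC0-12 (SD 0.21, six per group) does reproduce: t(0.95, 10) × 0.21 × √(2/6) = 1.812 × 0.21 × 0.577 = 0.22, and 1.50 ÷ and × exp(0.22) gives 1.20 to 1.87.

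**1. What each structure fits.** For one subject with values in Periods 1 and 2:

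- Text (UN by subject): variances v1 and v2, covariance c. The variance of the mean difference is (v1 + v2 − 2c)/n.
- Code as printed (UN by subject within population): v1 and v2 only. The variance of the mean difference is (v1 + v2)/n.

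Both structures were fitted by REML to one simulated set of six pairs, coding the likelihood directly because SAS was not available:

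| Structure | v1 | v2 | c | Difference | SE |
|---|---|---|---|---|---|
| UN | 0.0508 | 0.0677 | 0.0480 | −0.1411 | 0.0613 |
| UN with GROUP= | 0.0508 | 0.0677 | 0 | −0.1411 | 0.1405 |

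The first SE equals the paired SE, √((0.0508 + 0.0677 − 0.0959)/6). The second equals the two-sample SE, √((0.0508 + 0.0677)/6). The point estimate is identical.

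**2. Effect on width.** The within-subject correlation ρ is not given, so a range is shown. With equal variances V in the two periods:

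- printed code: half-width = t(0.95, 2n−2) × √(2V/n)
- paired: half-width = t(0.95, n−1) × √(2V(1−ρ)/n)
- ratio = t(0.95, 2n−2) / [t(0.95, n−1) × √(1−ρ)]

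The t values are 1.860 and 2.132 for n = 5, and 1.812 and 2.015 for n = 6.

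| ρ | Width ratio, n=5 | Width ratio, n=6 | Coverage of nominal 90% CI, n=5 | Coverage, n=6 |
|---|---|---|---|---|
| 0 | 0.87 | 0.90 | 90.7% | 90.5% |
| 0.2 | 0.98 | 1.01 | 93.4% | 93.3% |
| 0.5 | 1.23 | 1.27 | 96.9% | 97.0% |
| 0.8 | 1.95 | 2.01 | 99.4% | 99.5% |

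Coverage is that of the printed code, from 200,000 simulated bivariate normal data sets per cell with Satterthwaite degrees of freedom. The paired model gives 90% throughout. The widths are equal at ρ = 1 − (1.860/2.132)² = 0.24 for n = 5, and 1 − (1.812/2.015)² = 0.19 for n = 6.

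**3. Illustration, n = 5.** Assume a CV of 30% (the 15% of protocol section 11.2.1, doubled as that section does for severe impairment) and an observed GMR of 0.80. Then V = ln(1 + 0.30²) = 0.0862.

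| Model | Half-width (log) | 90% CI for GMR |
|---|---|---|
| Printed code | 1.860 × √(2 × 0.0862/5) = 0.345 | 0.57 to 1.13 |
| Paired, ρ = 0.2 | 0.354 | 0.56 to 1.14 |
| Paired, ρ = 0.5 | 0.280 | 0.60 to 1.06 |
| Paired, ρ = 0.8 | 0.177 | 0.67 to 0.95 |

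Neither the CV nor the GMR in this example is a Part 2 figure from the documents.

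**The case against.** The strongest reply is that nothing shows the error reached an analysis. The block is labelled as sample code, the protocol text is right, and the SAP says in the past tense that the correlation was modelled. Other sample code is also loose: the Part 1 regression code uses alpha=0.1 where the text asks for 95% limits. This stands in part, and no claim is made here about what was run. It does not settle the matter, because the SAP shows no code and section 9.9 reports no relevant change to a protocol that contains both the text and the contradicting line.

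Second, little turns on the interval: the GMR is unchanged, no hypothesis is tested (SAP section 9.8.3.3), no decision bound is attached, and the dialysis parameters are untouched. All true. It limits the weight of the point, but it is not a reason to leave a wrong line in the specification of a primary objective.

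Third, the width ratios use 2n−2 degrees of freedom, whereas a model with separate variances estimates fewer. The 2n−2 value is exact only when the two observed variances are equal. With Satterthwaite degrees of freedom (about 6.9 on average for n = 5, rather than 8, at low ρ), the simulated ratios of mean widths for n = 5 are 0.92, 1.03, 1.29 and 2.00 at ρ = 0, 0.2, 0.5 and 0.8, and break-even falls to about 0.15. This correction is fair and makes the loss slightly larger.

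Fourth, the error is conservative only under positive correlation. That is also right: at ρ = −0.3 the printed code covers about 86% for both n = 5 and n = 6. Positive correlation is plausible for two doses in one person, but the documents do not give it.

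**Conclusion.** The concern holds. As printed, the Part 2 code contradicts the text above it and fits a paired comparison as two independent samples. If it was run, the GMR and the geometric means stand (given complete pairs), but the 90% interval for the ratio is not the one described. For a positive correlation it covers more than 90%: about 97% at ρ = 0.5 and over 99% at ρ = 0.8. It is then about 1.2 to 2 times as wide as the paired interval; at low correlation the widths hardly differ. These sizes rest on equal period variances, normality on the log scale, an assumed range of ρ, and the standard reading of GROUP=, which was checked by REML outside SAS. If the code actually run omitted GROUP=, only the protocol's code block is wrong.

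A lesser wording point: a model with separate variances has no single mean square error, so that phrase does not describe how the 90% limits arise.

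**What to change.** 1. Replace the REPEATED line in protocol section 11.2.3.3 with `repeated population / type=UN subject=subject;`, without GROUP=.
2. Request the two confidence levels separately: `lsmeans population / cl alpha=0.05;` for the means and `estimate 'Period 2 - Period 1' population -1 1 / cl alpha=0.1;` for the difference. The coefficients require Period 1 to be the first level. Default alphabetical ordering would put the dialysis level first under the SAP's labels (ESRD HD, ESRD Non-HD) and invert the ratio, so use a numeric period code or set the level order explicitly.
3. In protocol sections 11.2.3.2 and 11.2.3.3 and SAP section 9.8.3, replace the reference to the mean square error with the model-based standard error of the difference and Kenward-Roger degrees of freedom.
4. Confirm which code was run. Only if GROUP= was used, rerun the Part 2 comparison for the five-subject and six-subject sets and replace the 90% intervals.

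The cost is one code line, two output statements and one phrase, with at most one rerun. No further patients or data are needed.
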